The retrospective part of the I³LUNG project includes the analysis of a multicentric retrospective cohort of more than 2,000 patients. This cohort will be used to perform a preliminary knowledge extraction phase and to build a retrospective predictive model for IO (R-Model), that will be used in the prospective study phase to create a first version of the Physician Decision Support System (PDSS) tool, an AI-based tool to provide an easy and ready-to-use access to predictive models, increasing care appropriateness, reducing the negative impacts of prolonged and toxic treatments on wellbeing and

	
healthcare costs. Also, CT and PET scans will be collected and a first radiomic signature will be created to feed the R-Model.
 
The prospective part of the project includes the collection and the analysis of multi-OMICs data from a multicentric prospective cohort of about 200 patients. This cohort will be used to validate the results obtained from the retrospective model through the creation of a new model (P-Model), which will be used to create the final Physician Decision Support System (PDSS) tool.

	
Overall Primary Objective

	
 • Prediction of response to immune checkpoint inhibitors in NSCLC by using clinical, biological, metabolomics, genomics, pathomics and radiomics data.
	
Secondary Objectives

	
 • Prediction of Progression-free survival (PFS) in response to immune checkpoint inhibitors in NSCLC by using clinical, biological, metabolomics, genomics, circulomics, pathomics, microbiome and radiomics data.
	
 • Prediction of Objective Response Rate (ORR) in response to immune checkpoint inhibitors in NSCLC by using clinical, biological, metabolomics, genomics, circulomics, pathomics, microbiome and radiomics data.
	
 • Prediction of Overall survival (OS) in response to immune checkpoint inhibitors in NSCLC by using clinical, biological, metabolomics, genomics, circulomics, pathomics, microbiome and radiomics data.
	
Exploratory Objectives

	
 • Added value of PET/CT into the prediction model for the Primary and Secondary Objectives.
	
 • Prediction of adverse events to immune checkpoint inhibitors in NSCLC by using clinical, biological, genomics, pathomics and radiomics data.

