	
RETROSPECTIVE PHASE:
 
The study cohort consists of aNSCLC patients treated with IO. Data from an estimated 2000 patients treated with IO-based therapy (any treatment line) in the period 2012-2021 will be collected from all the clinical partners (INT, GHD, VHI, MH, SZMC and UOC). Inclusion criteria will be checked and informed consent for the study and for the re-use of prior collected medical data will be obtained before enrolment. If not feasible, i.e. patients not alive, the approval to Privacy Guarantee will be obtained.

	
Inclusion criteria retrospective phase:
 
 1. Age \geq 18 years 2. Presence of an Eastern Cooperative Oncology Group (ECOG) performance status \leq 2; 3. Histologically confirmed diagnosis of stage III-IV Non-Small-Cell Lung Cancer patients receiving also maintenance therapy with durvalumab or other immune/combination are allowed; 4. Patients who received any line of IO-based therapy (immunotherapy monotherapy or immunotherapy in combination with any other treatments); 5. Patients with any CNS mets (stable or not) are allowed.

		OBSERVATIONAL STUDY PROTOCOL	MOD-PRO-G-03- DSC-10
--	---	---	---------------------------------

6. Patients with driver alteration (e.g., EGFR, BRAF, KRAS mutations or ALK, ROS1) who underwent an immunotherapy line will be included.

Exclusion criteria retrospective phase:

1. Patients without minimal treatment information data (e.g. start and stop date of immunotherapy and type of immunotherapy agent or protocol name)

PROSPECTIVE PHASE:

In the prospective phase, the study cohort consists of aNSCLC patients candidate for first-line IO-based therapy with available surgical samples (enough to perform OMICs). Baseline data of an estimated 200 patients from 5 clinical centers (INT, GHD, VHIO, MH and SZMC) will be collected including complete clinical, multi- OMICs analysis, imaging of CT and PET scan at baseline IO, behavioral, health economic, QoL measurements with based-sensor techniques and standard QoL. Data treated with IO-based therapy (any treatment line) will be collected. Inclusion criteria will be checked and informed consent for the study and for the re-use of prior collected medical data will be obtained before enrolment.

Inclusion criteria for prospective phase:

1. Age ≥ 18 years.
2. Evidence of a personally signed and dated ICF indicating that the patient has been informed of and understands all pertinent aspects of the study before enrolment.

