3. Eastern Cooperative Oncology Group (ECOG) performance status " 0-2.
4. Histologically confirmed diagnosis of stage IIIB/C-IV Non-Small-Cell Lung Cancer
5. No activating EGFR mutations or ALK/ROS1 rearrangements
6. No prior treatment for advanced disease
7. Availability of at least 1 (one) FFPE block for -omics data generation (for cohort 200 pts)
8. Clinical indication for frontline treatment with immunotherapy (alone or in combination), as first line of treatment for metastatic disease or consolidation treatment for locally advanced disease
9. Patients with untreated or unstable CNS brain metastases are allowed

Exclusion criteria for prospective phase:

1. Prior systemic treatment for NSCLC for advanced disease
2. Absence of sufficient amount of tumor tissue for -omics data generation for OMIC cohort (200 pts).
3. Unavailability or inability to comply with the requested study procedures, including compilation of QoL questionnaires and behavioral data collection (mobile app).
4. Unable to participate in the psychological study

	
Data for -omics analysis from patients considered screening-failure and, therefore, not eligible for the prospective phase of the protocol, will also be collected to feed the AI models using their real-world data generated during IO-based treatments. There is no limit for sample size in this phase and are not counted within the 200 patients who will be eligible for the multi-OMICs analysis.
																				
	
Scientific Clinical Study Design
 
I³LUNG will conduct an observational retrospective/prospective multicenter international project on advanced Non-Small-Cell Lung Cancer patients treated with IO. Its main objective is to study, train and validate the predictive accuracy of ML methods created by using real world data and multi-OMICs analyses, compared to the current standard of care biomarkers (e.g., the PD-L1).
 
The prospective study part of the project will start at month 3 and will continue up to 36 months, NSCLC patients candidates (n=200) to first-line IO-based therapy with available surgical samples (enough to perform -omics) will be enrolled.
 
In particular, will be collected the following data for Retrospective Phase (when available) and for Prospective phase:
																				

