	
(squamous vs non-squamous), Stage (III vs IV), PD-L1 status, and treatment administered (Chemo-Immuno vs immuno-alone vs others IO combinations) will be considered.
 
AI analysis plan
 
After Ethical approval in each Cancer Center, the third part of the study will start at month 3 and will continue up to 36 months. These periods will allow sufficient time for prospective enrolment and follow-up of patients for at least for 18 months. At month 30, an intermediate version of the P-Model will be released after the collection of the first batch (~100) of patients including multi-OMICs data. At months 54, after the predictive models are build using all the data from 200 patients, the final P-Model will allow to verify if: (i) new predictive system using multi-OMICs results perform better compared to current ones (e.g., PD-L1 or other state of the art biomarkers), (ii) if the model using -omics data perform better compared to the R model, (iii) if there is any specific -omics analysis which perform better compare to other -omics, which would give more value to the model (iv) if the P-Model perform better compared to current biomarker, and compare to the R-model when applied to specific subgroups of patients (e.g., non-squamous vs squamous patients). We will consider this phase successful if the new P-models outperforms current biomarkers prediction at least for 10% in terms of correct prediction of either 2-year PFS and 2-year OS, measured with Harrel's C statistic.

	
The study is conducted in accordance with the Declaration of Helsinki Ethical Principles and Good Clinical Practices and was approved at each site by an independent local ethics committee.
 
During the clinical visit, after receiving adequate study information, the patient may sign an informed consent form, in accordance with the provisions of the local ethical regulations. The consent of the patient must be signed and personally dated by the patient and by the investigator/person designated to conduct the informed consent discussion. The signed and dated declaration of informed consent will remain at the researcher site and must be safely archived by the investigator so that the forms can be retrieved at any time for monitoring, auditing and inspection purposes. A copy of the signed and dated information and consent should be provided to the patient prior to participation.

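### Comparing the P-Model with the R-Model cannot isolate the value of omics, because training population and data quality change together with the omics input, and the bias can run either way

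*Protocol*

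**What the plan says.** Question (ii) of the Protocol's AI analysis plan asks "if the model using -omics data perform better compared to the R model". Question (iv) repeats the comparison with the R-Model within subgroups. Question (iii) compares omics layers with each other.

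Background and Rationale says the retrospective cohort will be used to "build a retrospective predictive model for IO (R-Model"). The retrospective population is described as "Data from an estimated 2000 patients treated with IO-based therapy (any treatment line) in the period 2012-2021". Its inclusion criteria admit:

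- "Histologically confirmed diagnosis of stage III-IV Non-Small-Cell Lung Cancer"
- "Patients who received any line of IO-based therapy (immunotherapy monotherapy or immunotherapy in combination with any other treatments")
- "Patients with driver alteration (e.g., EGFR, BRAF, KRAS mutations or ALK, ROS1) who underwent an immunotherapy line will be included"

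The prospective inclusion criteria require "No activating EGFR mutations or ALK/ROS1 rearrangements" and "No prior treatment for advanced disease", and restrict stage to IIIB/C-IV. Five of the six centres take part in the prospective phase.

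The P-Model is introduced as a new model from the prospective cohort, and the AI analysis plan has the final models built with all 200 patients. The prospective-phase objectives also say that prospective data will feed models learned on retrospective data and that the two data sets will be integrated. The Protocol therefore leaves open whether the P-Model is fitted on the 200 alone or on both sources.

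**The concern.** A claim that omics add predictive value needs two models that differ only in the omics. Here several things change at once: the omics input, exposure to the target population, the completeness of the data (the baseline data table labels the retrospective column Jeopardized and the prospective one Homogenized), and some non-omics inputs such as lifestyle factors, which are collected only prospectively. The prospective objectives also plan to refine the radiomic signature on prospective images, so non-omics inputs are themselves retuned between the two models.

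No model without omics, trained on the same data as the P-Model, is named as comparator. At stake is the conclusion on whether a costly multi-omics work-up earns its place in the final decision tool. A favourable P versus R result could come from retraining alone. An unfavourable one could hide a real omics contribution, because the R-Model rests on about ten times as many patients (2000 / 200 = 10).

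**Working it through.** The Protocol states no effect size, power or margin for P versus R, so there is no figure of its own to reproduce. The 0.1 AUC increase in the sample size section belongs to the comparison with validated biomarkers and is not a benchmark here.

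**Decomposition.** For AUC (or C) measured in the same prospective patients,

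P − R = (P with omics − P without omics) + (P without omics − R).

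The first bracket is the omics question. The second is retraining and data quality. Question (ii) reports only the sum.

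**Illustration.** All inputs are assumptions except the two sample sizes, 2000 and 200:

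- Eight clinical predictors.
- A ridge logistic R-Model fitted on 2000 patients.
- A P-Model fitted on 200 patients with the same eight predictors plus omics features whose true effect is zero.
- Both models scored on 4000 new patients from the prospective population, 300 replicates.
- ρ is the similarity (cosine) of the clinical effects in the two populations.

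Mean AUC with five null omics features:

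| ρ | R | P without omics | P with null omics | Omics bracket | Retraining bracket | P − R |
|---|---|---|---|---|---|---|
| 1.0 | 0.738 | 0.719 | 0.706 | -0.013 | -0.019 | -0.032 |
| 0.9 | 0.713 | 0.719 | 0.707 | -0.012 | +0.006 | -0.006 |
| 0.7 | 0.664 | 0.720 | 0.708 | -0.012 | +0.056 | +0.044 |
| 0.5 | 0.616 | 0.719 | 0.707 | -0.012 | +0.103 | +0.091 |
| 0.3 | 0.570 | 0.719 | 0.707 | -0.012 | +0.149 | +0.137 |

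The omics bracket is constant and slightly negative, which is correct for useless features that cost estimation precision. P − R changes sign solely because ρ changes.

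**More noise features.** With 50 null features and a ridge penalty of 30 instead of 1, P with omics falls to about 0.645. P − R is then 0.645 − 0.738 = -0.093 at ρ = 1.0, 0.646 − 0.664 = -0.018 at ρ = 0.7 and 0.646 − 0.569 = +0.077 at ρ = 0.3.

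**Updating instead of refitting.** If the R-Model score enters the P-Model as an input, with five null features, P − R is 0.707 − 0.738 = -0.031 at ρ = 1.0 and 0.708 − 0.664 = +0.044 at ρ = 0.7, nearly the same as above. Straight pooling was not simulated. The prospective patients would then be 200 / 2200 = 9% of the training data, so without extra weighting the retraining part would probably be smaller. The two models would still not share training data.

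**The case against.** **Different populations need not mean wrong weights.** Mutational status, stage, previous treatments and first-line regimen are all listed for retrospective collection, so the R-Model could condition on untreated, driver-negative status. The cohorts also overlap: KRAS- and BRAF-altered patients are not excluded prospectively. This stands, and it means similarity may be high. But at high similarity the retraining part turns negative, so the contrast is still not a measure of omics.

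**Question (ii) may only ask whether the second tool beats the first.** The R-Model feeds the first version of the physician tool and the P-Model the final one, and P versus R answers that fairly. This stands too. It does not support reading the answer as the value of omics, which the wording of (ii) invites.

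**The P-Model may be pooled or updated, and screening failures may also feed the models.** True, but a P-Model of either kind has still seen prospective patients whom the R-Model has not.

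**Folds, resampling and intervals can be left to a statistical analysis plan, which is not shown.** Agreed. The point is the comparator that the Protocol names, not missing detail.

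A reader might infer something stronger: that retraining is bound to be credited to omics. A simple binormal calculation seems to show this. If correctly weighted clinical and radiomic data have AUC 0.70, an R score correlating ρ with the ideal score has AUC Φ(ρ·Φ⁻¹(0.70)) = 0.682, 0.663, 0.643 and 0.623 for ρ = 0.9, 0.8, 0.7 and 0.6, an apparent gain of 0.02 to 0.08. The arithmetic is right, but it grants the refitted model its ideal AUC with no cost for learning from 200 patients, so the P-Model cannot lose. The documents give no value for ρ and do not fix the direction.

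**Conclusion.** The point holds as one of attribution. By the Protocol's own eligibility criteria and data table, question (ii) and the R-Model part of (iv) vary omics input, training population and data quality together, so P minus R cannot be read as the contribution of omics in either direction.

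The size is unknown. The span of -0.03 to +0.14 AUC with five useless omics features is illustrative and rests on assumed similarity, signal strength and feature numbers; more noise features shift it downward. The conclusion that the contrast is confounded does not depend on those figures.

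The issue does not touch the success criterion against current biomarkers, nor does it fault a broad training set for the R-Model. It should be corrected but does not threaten the study's main comparison.

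**What to change.** Keep P versus R, described as a comparison of two tools. Answer the added-value question separately:

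- Fit the same algorithm with and without omics on the same training data: either the prospective patients, with the R-Model score allowed as an input to both fits, or the same pooled data for both.
- Evaluate both fits on the same held-out or cross-validated prospective patients.
- Report the paired difference in AUC and in Harrell's C with a confidence interval.
- Use the same pair for any subgroup statement about omics under question (iv).
- State whether the P-Model is fitted on the 200 alone or on both data sets.
- Optionally, show an R-Model trained on the first-line, driver-negative retrospective subset as a sensitivity analysis.

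Fix this before the intermediate P-Model at month 30, so that the comparator is not chosen after results are seen. It needs extra model fits on data already planned, and no new patients or samples. The drawback is that the estimated omics gain may be smaller than P versus R would suggest.

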	Cytokines and MicroRNA signature (MSC test)		✓
	Cell free DNA and ctDNA sequencing		✓

 
— Sistema Socio Sanitario Regione Lombardia
		OBSERVATIONAL STUDY PROTOCOL	MOD-PRO-G-03- DSC-10
---	---	---	---------------------------------

Genomics analysis: tumor mutational burden (TMB), somatic copy number alterations, whole genome sequencing, immune infiltration transcriptomic profile		✓
Metabolomics and Microbiome		✓

The clinical/synthetic data will be collected within i3LUNG web-based platform. To each patient will be assigned a code. The CRF form will be filled in from each center with a dedicated account and all these workflows will be addressed using the Data Management Plan.

In particular, for the prospective phase the following multi-OMICs data will be collected for all 200 patients with available tissue and blood. For details see Table 2.

Omics type	Collection	Analyses
Tissue-based (Tasks 3.2, 3.3, 3.4)	Formalin-Fixed Paraffin Embedded (FFPE) tissue blocks from NSCLC patients who underwent surgery or large biopsy will be collected. Every 5 collected samples, FFPE blocks will be shipped to GHD. GHD will then extract samples for immune profiling/TME and will prepare 4 total cores, 2 for genomic profiling and 2 for metabolomics.	
 TME and Tissue Immune Profiling - Reference tissue spots with known expression of the target proteins will be added to each microenvironment Tissue Microarrays (ME-TMA) Genomic profiling (DNA and RNA extraction) and transcriptomics profiling. Metabolomics, metabolite extraction for targeted and untargeted metabolomics analysis

Commentato [CP1]: [name] please check the tubes of WB.

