Sample size and statistical analysis and AI analysis plan	
For the retrospective phase, we have planned to enroll patients based on a first check availability of already treated patients with IO-based therapy among centres.
 
The primary objective of the study is to compare the predictive accuracy of ML methods (created using multi-OMICs analyses) with current validated biomarkers (e.g., PD-L1 or available scores, see Table 2). Considering the number of 200 prospective cases, the study will have at least 85% power to detect a 0.1 increase in predictive accuracy as measured by the area under the ROC curve (AUC), assuming an AUC for validated biomarker alone of at least 0.6, using a one-sided z-test at a significance level of 0,050. The data are assumed to be discrete (rating scale) responses. Stratification Factors: Country (Italy or others), Gender (male vs females), ECOG PS (0-1 vs 2), Histology

---	--

 
Sistema Socio Sanitario Regione Lombardia
		OBSERVATIONAL STUDY PROTOCOL	MOD-PRO-G-03- DSC-10
---	---	---	---------------------------------

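### The prospective phase is sized on an AUC test but judged on a 10% gain in Harrell's C; the protocol does not link the two, and the success rule has conflicting readings

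*Protocol*

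**What the plan says.** **Sizing.** The sample size section states that 200 prospective cases give "at least 85% power to detect a 0.1 increase in predictive accuracy as measured by the area under the ROC curve (AUC"). The test is a one-sided z-test at 0.05, and the baseline is set by "assuming an AUC for validated biomarker alone of at least 0.6". The section adds that "The data are assumed to be discrete (rating scale) responses". It does not say which outcome the AUC classifies. The comparator is given as "current validated biomarkers (e.g., PD-L1 or available scores, see Table 2").

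**Success.** The AI analysis plan, in the same row of the protocol, says the phase succeeds if the P-Model "outperforms current biomarkers prediction at least for 10% in terms of correct prediction of either 2-year PFS and 2-year OS". Performance on these two outcomes is to be "measured with Harrel's C statistic". It gives no test, significance level or confidence bound for this rule. The models are to be built on the data of all 200 patients.

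**Endpoints.** The prospective-phase objective and the sample size section both make the comparison with biomarkers primary. Under Study Endpoints, the primary endpoint is only that a model will be developed, with no performance measure. PFS and OS appear as secondary objectives and secondary endpoints.

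**The concern.** One comparison in one phase has two criteria that differ in metric (AUC or Harrell's C), in outcome (unnamed, or 2-year PFS and OS) and in decision rule (a test against zero gain, or a minimum gain of 10%). Neither is said to govern the primary conclusion, and the primary endpoint does not settle it.

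The success rule is also open in two places. The 10% may be absolute or relative, and *either … and* may mean one endpoint or both. If these choices are made after the results are known, the same data could be reported as a success or a failure. The tool is meant to guide therapeutic choice and is headed for CE marking, so that freedom matters.

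**Working it through.** **Inputs from the protocol:** n = 200; AUC 0.60 versus 0.70; one-sided 0.05 (z = 1.645); success threshold 10%.

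**Inputs not given, so assumed over a range:** share of patients with the event, 30–70%; correlation r between the two AUCs in the same patients, 0–0.6. The model is treated as a fixed index, with no allowance for optimism.

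**1. The plan's own 85%.** The Hanley–McNeil variance is V(A) = [A(1−A) + (n1−1)(a−A²) + (n0−1)(b−A²)]/(n1·n0), with a = A/(2−A) and b = 2A²/(1+A). At 100 events and 100 non-events, V(0.60) = 0.001594 and V(0.70) = 0.001357.

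SE = √[V(0.60) + V(0.70) − 2r√(V(0.60)·V(0.70))]. At r = 0.5, SE = √(0.002951 − 0.001471) = 0.0385.

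Power = Φ(0.1/SE − 1.645). At r = 0.5 this is Φ(2.60 − 1.645) = 83%.

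| Events | r = 0 | 0.3 | 0.4 | 0.5 | 0.6 | r needed for 85% |
|---|---|---|---|---|---|---|
| 50% | 58% | 71% | 77% | 83% | 90% | 0.53 |
| 70% | 55% | 68% | 73% | 80% | 87% | 0.57 |
| 30% | 49% | 62% | 67% | 74% | 82% | 0.63 |

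If the cut-off uses the null SE, √[2V(0.60)(1−r)], power at 50% events and r = 0.5 is 81%, and 85% needs r of about 0.55. A rating-scale (binormal) variance gives nearly the same results. The 85% is therefore attainable, but only under inputs the protocol does not state.

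**2. The test and the success rule can disagree.** At 50% events and r = 0.5 the test is significant from an observed gain of 1.645 × 0.0385 = 0.063 (0.066 with the null SE). An observed gain of 0.08 passes the test and misses an absolute bar of 0.10. At 30% events and r = 0 the null-SE cut-off is 0.104, so an observed gain of 0.10 meets the bar without being significant.

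**3. The readings of the rule disagree.** At a biomarker C of 0.60 the bar is 0.70 if absolute and 0.66 if relative. Suppose C rises from 0.60 to 0.67 on PFS (+0.07; 0.07/0.60 = 11.7%) and from 0.60 to 0.65 on OS (+0.05; 0.05/0.60 = 8.3%).

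- Relative, one endpoint enough: success.
- Relative, both needed: failure.
- Absolute, one or both: failure.

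**4. Chance of meeting the rule as a point threshold**, one endpoint, on the AUC scale as a stand-in for C, at 30–50% events and r = 0–0.6:

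- *Absolute, true gain 0.10.* The threshold equals the true gain, so the chance is about 50% whatever the SE. For two endpoints whose observed gains correlate at ρ, P(both) = 1/4 + arcsin(ρ)/(2π). This gives 25, 33 and 40% at ρ = 0, 0.5 and 0.8; either one then gives 75, 67 and 60%.
- *Relative (bar 0.06), true gain 0.10.* Φ(0.04/SE) runs from Φ(0.04/0.0616) = 74% to Φ(0.04/0.0344) = 88%.
- *Relative, no true gain.* 1 − Φ(0.06/SE₀), where SE₀ is the null SE, runs from 5% (SE₀ = 0.0357) to 17% (SE₀ = 0.0632).

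**5. Illustrative check on Harrell's C itself.** A simulation assumed median PFS 8 months, median OS 18 months, biomarker–model correlation 0.5, censoring uniform over 18–54 months, and true C of about 0.59 versus 0.69. The absolute rule was met in 61% of runs (either endpoint) or 37% (both); the relative rule in 96% or 89%. With no true gain, the relative rule was met in 2% (PFS) and 5% (OS). The readings differ in the same direction, but the levels are not those of the AUC scale.

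**The case against.** The strongest reply is that nothing here strictly conflicts. Success is defined once, in the AI analysis plan. The sample size section says only what difference 200 patients can detect. A powered test and a performance target can coexist, and Harrell's C is the censored-data counterpart of the AUC, so 0.1 and 10% may be one target, with the absolute reading favoured. A statistical analysis plan could add a bound. This stands to the extent that the two criteria are unlinked rather than incompatible. It does not remove the point: the protocol fixes both criteria, does not say they are one target, and even then power to show a gain above zero is not the chance of observing a gain of 0.10.

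A reader might go further in three ways that the protocol does not support.

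- *That the 85% is an arithmetic error.* It is not; plausible correlations and event shares reach it.
- *That the study has only a 50% chance of success.* Any point threshold set at the true effect is met about half the time. The figure belongs to the absolute reading, one endpoint and a true gain of exactly 0.10, and the protocol does not say that the rule is a bare point estimate.
- *That 18 months' follow-up invalidates the 2-year rule.* The plan promises "follow-up of patients for at least for 18 months", short of 24, but Harrell's C accommodates censoring. This would matter only for a binary 2-year status.

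The comparator's table reference is also minor. Elsewhere the protocol cites the same table number for the omics collection, "for all 200 patients with available tissue and blood. For details see Table 2", so the pointer looks misdirected. The tables as available carry no captions, so it needs checking rather than a conclusion.

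**Conclusion.** The point holds as an unlinked pair of criteria together with an ambiguous success rule. The stated 85% is the power of an AUC test on an unnamed outcome, not of the rule that decides success. Which criterion and which reading apply can reverse the conclusion on the same data, as the worked examples show without any assumption beyond a biomarker value of 0.60 and, for the AUC test, 50% events and r = 0.5.

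The probabilities are conditional: they treat the rule as a point threshold, use the AUC scale for C, and rest on assumed event shares and correlations. They show that the readings differ materially; they do not forecast the study's result. Severity: should-fix.

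**What to change.** 1. State which criterion governs the primary conclusion. Either use one metric, one outcome and one named comparator for both sizing and success, or make the AUC test on a named outcome confirmatory and call the 10% gain in C a secondary performance target.
2. State whether 10% is absolute or relative. Replace *either … and* with one endpoint, or with an explicit either/both rule with multiplicity control.
3. Base the success decision on a paired confidence bound for P-Model minus comparator, computed on held-out, cross-validated or optimism-corrected predictions. A bound from the same 200 patients used to build the model would otherwise be too favourable. Whether a 10% minimum gain is kept beside the bound is the sponsor's choice.
4. Restate the power for the governing criterion with its assumed correlation and event share. On the AUC test, 85% needs a correlation of about 0.53–0.55 at 50% events, and more if events are unbalanced. If Harrell's C governs, the power must be recomputed.
5. As a minor item, check the table reference for the comparator.

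The cost is protocol wording, a modest recalculation, and a power figure that becomes conditional and less favourable. The sample size stays at 200.
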